#### **8.10.3 Randomization**

Subjects will be randomized in a 1:1 ratio to receive screening by either CCE (using the PillCam® endoscopy system with PillCam® COLON 2 capsule) or CTC. The study will utilize randomization in blocks in order to allocate subjects into two arms:

- Group 1: CCE
- Group 2: CTC

Randomization will occur at the screening visit at the gastroenterology site, after eligibility has been confirmed and signed informed consent has been obtained. Due to the nature of the test and control screening procedures, neither the subject nor the investigator will be blinded to the assigned study arm.

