### 9.2 Primary Hypothesis Analysis

The primary statistical hypothesis is that the diagnostic yield (proportion of subjects having an actionable lesion, defined as any polyp or mass lesion  $\geq 6$  mm) will be noninferior for CCE compared to CTC in a screening population, that is,  $H_0: p_1 \leq p_0 - \delta$  versus  $H_a: p_1 > p_0 - \delta$  where  $p_1$  and  $p_0$  are the diagnostic yield rates for CCE and CTC respectively. The non-inferiority margin ( $\delta$ ) is pre-defined to be 5%.

The probability of  $(p_0 - p_1 < \delta)$  will be computed from the posterior distribution of the difference  $(p_0 - p_1)$ . Should the posterior probability  $\Pr(p_0 - p_1 < \delta | Data)$  be at least 98% at the interim or 96% at the final analysis, then the null non-inferiority hypothesis will be rejected, and non-inferiority of CCE to CTC will be claimed. The probabilities of 98% (interim) and 96% (final) are chosen to ensure the false positive rate (type I-like error) is well controlled.

If the non-inferiority of CCE to CTC is established with respect to the diagnostic yield, a superiority test will also be performed. The null superiority hypothesis is  $H_0: p_1 \leq p_0$ , and the alternative superiority hypothesis is  $H_a: p_1 > p_0$ . The probability of  $(p_1 > p_0)$  will be computed from the posterior distribution of the difference  $(p_1 - p_0)$ . If the posterior probability  $\Pr(p_1 > p_0 | Data)$  is at least 98% (interim) or 96% (final), then the null superiority hypothesis will be rejected and superiority of CCE to CTC will be claimed.

If the interim non-inferiority analysis does not meet the pre-defined success criteria, there will be no early claim for success and the study will continue until completion.

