#### 9.5 Analysis Populations

The primary effectiveness analysis will be based on all randomized subjects without major protocol deviations (defined to be protocol violations that may have a significant impact on subject outcomes) and who don't meet any of the following criteria:

1. Subject withdraws
2. Capsules remained in the stomach or small bowel during the entire procedure
3. Optical colonoscopy could not be done
4. System technical failure

A confirmatory effectiveness analysis will be conducted on a modified intent-to-treat (mITT) population, including all randomized subjects with CTC or CCE. In the unlikely event that a subject receives the incorrect procedure, the subject will be included in the analysis using the procedure that is actually received. All other effectiveness endpoints will be analyzed based on the mITT population. Safety evaluation will be based on all study subjects accordingly to procedures actually received.

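### The plan names no analysis set for superiority and gives the mITT result no bearing on either claim, so exclusions that fall mainly on CCE can produce a superiority claim that the as-randomized data do not support

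*Combined protocol and SAP*

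**What the plan says.** Section 9.2 (Primary Hypothesis Analysis) sets two decision rules on the primary endpoint. Non-inferiority is claimed if the posterior probability that the CTC yield exceeds the CCE yield by less than 5 points should "be at least 98% at the interim or 96% at the final analysis". Superiority follows: "If the non-inferiority of CCE to CTC is established with respect to the diagnostic yield, a superiority test will also be performed". If the posterior probability that the CCE yield exceeds the CTC yield "is at least 98% (interim) or 96% (final), then the null superiority hypothesis will be rejected". Neither rule names an analysis set.

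Section 9.5 (Analysis Populations) supplies the sets. "The primary effectiveness analysis will be based on all randomized subjects without major protocol deviations", and four further exclusions apply: withdrawal, OC that could not be done, system technical failure, and "Capsules remained in the stomach or small bowel during the entire procedure". A second analysis is then described: "A confirmatory effectiveness analysis will be conducted on a modified intent-to-treat (mITT) population, including all randomized subjects with CTC or CCE". Subjects in it are analysed by the procedure actually received. The section also says: "All other effectiveness endpoints will be analyzed based on the mITT population". It gives no threshold for the mITT result, no requirement that it agree with the primary set, and no rule for counting an mITT subject with a failed capsule or no OC.

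Section 8.10.3 records that "neither the subject nor the investigator will be blinded to the assigned study arm".

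**The concern.** Superiority is tested on the primary endpoint, so by inference it is decided in the primary set of section 9.5. The documents do not use the term, but this is a per-protocol set in substance. A capsule that stays in the stomach or small bowel has not examined the colon. As randomized, that subject is a CCE non-detection. Removing the subject takes one from the CCE denominator and nothing from its numerator, and no CTC subject can meet that criterion. Major deviations, the most open-ended exclusion, are judged in a trial where the arm is known.

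Two consequences follow. Superiority could be claimed because of who was removed rather than because the capsule found more lesions per subject assigned to it. Either claim could also stand beside an mITT result that fails the same threshold, and nothing in the plan says what would then happen.

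**Working it through.** **Inputs.** From section 9.1: yields 25% (CCE) and 15% (CTC), margin 5 points, looks every 40 per arm up to 160 per arm, about 10% attrition, stated power above 80%. From section 9.2: thresholds 98% (interim) and 96% (final). From section 9.6: stop when non-inferiority is met. Assumed, because the documents are silent: a Beta(1,1) prior, looks counted in randomized subjects, exclusion fractions by arm, and excluded subjects having zero yield.

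**Step 1: the plan's own power.** Fixed-sample formula: power = Φ[(0.10 + 0.05)/SE − z], with SE = √[(0.25×0.75 + 0.15×0.85)/n].

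- n = 160: SE = √(0.315/160) = 0.0444. One-sided 0.05: 0.15/0.0444 − 1.645 = 1.74, so 95.9%.
- n = 144 (160 less 10%): SE = 0.0468, so 94.1%.

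Simulating the four-look rule gives 95.6% and 93.8%. The stated lower bound of 80% reproduces.

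**Step 2: what an exclusion does to the yield.** If a fraction f of an arm is removed and none of those removed had a yield, the yield in the primary set is the as-randomized yield divided by (1 − f). From 20%:

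- f = 5%: 0.20/0.95 = 21.1%.
- f = 10%: 0.20/0.90 = 22.2%.
- 8% of CCE and 2% of CTC: 0.20/0.92 = 21.7% against 0.20/0.98 = 20.4%.

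**Step 3: false superiority when as-randomized yields are both 20%.** Simulation of 200,000 trials per scenario; superiority is read at the look where non-inferiority is met.

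| Excluded, CCE vs CTC | Four-look rule | One final analysis, 160 per arm |
|---|---|---|
| None (all randomized) | 3.2% | 4.0% |
| 5% vs 0% | 4.3% | 6.4% |
| 8% vs 2% | 4.6% | 7.0% |
| 10% vs 0% | 6.0% | 10.0% |

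The four-look column is the planned design. Its rates are lower because most superiority readings occur at an interim look, at the 98% threshold. Separate runs differ by no more than about 0.2 points. Under the four-look rule, balanced exclusions (5%/5% or 10%/10%) leave the rate essentially unchanged, at about 3.2%. With 2% of CCE and 8% of CTC removed it falls to about 2.2%.

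**Step 4: false non-inferiority when CCE is truly 5 points worse (15% vs 20%).** Under the four-look rule the rate is about 6.8% in all randomized subjects and 11.9% in the primary set at 10% vs 0%. In one final analysis it goes from 4.1% to 8.5%. The 6.8% baseline belongs to the four-look rule with this assumed prior and is a separate matter; the point here is the increase.

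**Step 5: one dataset at the final look.** CTC 24/160; CCE 33 positives, with 16 non-positive CCE subjects excluded.

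- Primary set, 33/144: Beta(34, 112) against Beta(25, 137) gives a posterior of 96.1%. Superiority is claimed.
- All randomized, 33/160: Beta(34, 128) against Beta(25, 137) gives 90.4%. Superiority is not claimed; 37/160 would be needed (96.7%).

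The positives are the same in both. Only the denominator differs.

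**The case against.** The strongest reply is that this is a gap in wording with a small effect. Much of that is fair, and it limits what may be concluded.

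- A reader might infer that the mITT analysis has no role. Section 9.5 calls it confirmatory, so that goes too far. What is missing is a decision role: a threshold, or a consequence if it disagrees.
- A reader might say that the plan assigns superiority to a per-protocol set. Section 9.2 does not. The set is inferred from section 9.5, though a headline claim should not depend on inference.
- A reader might hold that such a set is anti-conservative for superiority in general. It is not. Inflation needs zero-yield exclusions that fall mainly on CCE. Three of the four listed criteria, and major deviations, can apply in either arm. Section 8.10.1 says that low eGFR is a problem for CTC and not for CCE, so losses could also fall on CTC. Incomplete passage through the colon is not a listed exclusion.
- A reader might take the 10.0% from a single final analysis as the size. The plan has four looks and stops at non-inferiority, and the matching figure is about 6.0%. At 5% vs 0% and 8% vs 2% the four-look rate stays below 5%.
- Scoring every missing OC as no yield would be open to dispute. OC is the reference standard in both arms, and its absence is not a failure of CCE or CTC.

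What survives is that one exclusion can only remove CCE subjects, and that nothing in the plan would stop a claim that the as-randomized data do not support.

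**Conclusion.** The concern holds in this limited form. Both claims rest, by inference, on a set that can lose CCE failures with no CTC counterpart, and the mITT analysis has no stated bearing on either. Under the planned four-look rule the cost is about 1 to 3 points of false superiority (from 3.2% to between 4.3% and 6.0%) and about 5 points of false non-inferiority at 10% vs 0% (6.8% to 11.9%).

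These figures rest on assumed exclusion rates, zero yield among those excluded, a Beta(1,1) prior and a 20% yield (for non-inferiority, 15% vs 20%). The only related figure in the documents is about 10% attrition overall. The effect is modest near 5%, material near 10%, absent if exclusions are balanced, and reversed if CTC loses more. The documents do not show that the trial's error rate will be inflated; they show that it is left unprotected. It is a cheap improvement worth making.

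**What to change.** In sections 9.2 and 9.5:

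1. State that superiority is decided in all randomized subjects, analysed as randomized, with a failed or unreadable CCE or CTC examination counted as no yield.
2. Handle missing OC by one prespecified rule applied equally to both arms, with a sensitivity analysis.
3. State that non-inferiority is claimed only if the posterior threshold is met in the primary set and also in this all-randomized set.

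The present mITT set cannot serve as it stands: it goes by procedure received, is limited to subjects who had CTC or CCE, and has no rule for failed or unconfirmed examinations.

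Cost, with primary-set yields of 25% and 15% and the three exclusion scenarios above under the four-look rule: non-inferiority power falls from about 95% to between 89% and 93%, still above the stated 80%. Superiority power falls from about 30% to between 21% and 26%, a loss of about 4 to 9 points on a test that section 9.1 already says is not powered at 80%. The change takes a few sentences and no extra patients.

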### 9.3 Effectiveness Analyses

All effectiveness variables will be summarized using descriptive statistics. The difference between treatment groups in categorical variables will be tested using two-sided Chi-square test or Fisher's exact test as appropriate. The difference between treatment groups in continuous variables will be tested using two-sided t-test or non-parametric Wilcoxon rank sum test as appropriate.

- Sensitivity, specificity, NPV, and PPV for the detection of polyps  $\geq 6$  mm and  $\geq 10$  mm (per subject) relative to the confirmatory OC exam
- [REDACTED]
- [REDACTED]
- [REDACTED]
- [REDACTED]
- [REDACTED]
- [REDACTED]
- [REDACTED]

- [REDACTED]
- [REDACTED]

#### 9.4 Safety Analysis

Individual listings of AEs, including type of device, AEs (reported term) start date, duration, severity, and procedure-relatedness will be provided. Procedure relatedness will be assessed separately relative to the imaging modality and colonoscopy, as described in Section 11.8.

AEs will be summarized using frequency counts and percentages. Descriptive statistics will be provided by study arm and by severity and relationship, according to the definitions in Section 11.8. Comparisons between treatments of the proportions of subjects experiencing at least one AE, at least one SAE, at least one CCE/CTC device/procedure related AE, and at least one colonoscopy procedure related AE will be made using Chi-square test or Fisher's exact test as appropriate.

#### 9.5 Analysis Populations

The primary effectiveness analysis will be based on all randomized subjects without major protocol deviations (defined to be protocol violations that may have a significant impact on subject outcomes) and who don't meet any of the following criteria:

1. Subject withdraws
2. Capsules remained in the stomach or small bowel during the entire procedure
3. Optical colonoscopy could not be done
4. System technical failure

A confirmatory effectiveness analysis will be conducted on a modified intent-to-treat (mITT) population, including all randomized subjects with CTC or CCE. In the unlikely event that a subject receives the incorrect procedure, the subject will be included in the analysis using the procedure that is actually received. All other effectiveness endpoints will be analyzed based on the mITT population. Safety evaluation will be based on all study subjects accordingly to procedures actually received.

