### 21.3 Appendix C3 – OC Procedure Instructions

The confirmatory OC will first be conducted blinded to the CCE/CTC results and then unblinded, if discrepancies in polyp detection are observed, as shown below. For the blinded OC procedure, the colonoscopist will be kept blinded to the CCE or CTC results until the OC procedure visualizes the entire colon. After the blinded colonoscopy, the colonoscopist will review the RAPID or CTC report with the CCE or CTC results. If results are not congruent, a second colonoscopy will be performed.

For both the blinded and unblinded OC studies:

- Study GI endoscopists (not the same GI physician that performs the local reading) will be trained by the sponsor on polyp size estimation using study designated biopsy forceps (Radial Jaw 4, by Boston Scientific), to confirm homogeneous methods between all participating study centers.
- The OC examination will be recorded electronically and sent to the sponsor. Only the subject study ID and initials should appear in the recorded video either by inserting the initials to the recording machine or by including a snapshot of the subject's initials written on a piece of paper at the beginning of the procedure. The withdrawal time will need to be at least 6 minutes as per common practice.
- Size measurement for every polyp using the reference forceps will be documented in a picture (i.e., open study forceps will be placed as close as possible to the polyp, on maximum linear dimension, while it is being photographed).
- All OC still pictures will be saved in a digital format (.tif or .bmp). Quality copies of the pictures taken during OC will be provided to the study sponsor with the OC report.
- These videos and pictures will be archived by the sponsor and may be used in future analyses to, for example, provide further information about observed lesions, to assess study quality, or add further information regarding comparisons between colonoscopy and capsule findings.

For each OC procedure the following information will be collected:

- Adequacy of colon preparation for each colorectal segment (cecum, ascending, transverse, descending/sigmoid, and rectum) and for the overall colon using a validated system, as shown in Appendix C4. This information should be recorded in the CRF.
- Colonoscopy report
- The following information will be collected and documented for each polyp detected:
  - Location: Colon segment (i.e., cecum, ascending, transverse, descending/sigmoid, and rectum)

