**21.4 Appendix C4 – OC Bowel Cleansing Scale**

**Cleansing Level Scale for Optical Colonoscopy**

Rating	Description
Poor	Inadequate
	Large amount of fecal residue precludes a complete examination
Fair	Inadequate, but examination completed
	Enough feces or turbid fluid to prevent a reliable examination
Good	Adequate
	Small amount of feces or turbid fluid not interfering with examination
Excellent	Adequate
	No more than small bits of adherent feces

Adapted from Leighton JA et al. Endoscopy 2011;43:123-7.

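### A completed colonoscopy graded Fair, which Appendix C4 itself calls inadequate and unreliable, still serves as the truth standard for yield and accuracy

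*Combined protocol and SAP*

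**What the plan says.** Sections 8.2 and 8.3 judge primary yield and the four per-subject accuracy measures against the confirmatory OC.

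Appendix C3 has the site record, for each OC, "Adequacy of colon preparation for each colorectal segment (cecum, ascending, transverse, descending/sigmoid, and rectum) and for the overall colon". The scale is in Appendix C4:
- Poor: "Large amount of fecal residue precludes a complete examination".
- Fair: "Inadequate, but examination completed", described as "Enough feces or turbid fluid to prevent a reliable examination".
- Good and Excellent are the two adequate grades.

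Section 9.5 sets the populations. The only colonoscopy condition for the primary set is "Optical colonoscopy could not be done". Major protocol deviations are also removed, defined as "protocol violations that may have a significant impact on subject outcomes". The mITT set is described as "including all randomized subjects with CTC or CCE", with no condition on the OC. On the accuracy measures, 9.5 says: "All other effectiveness endpoints will be analyzed based on the mITT population".

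Table 3 in Appendix E has four cells and no indeterminate class. An unmatched CCE or CTC polyp of 6 mm or more is a false positive. A subject whose reported polyps are all below 6 mm is a true negative.

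The plan has one safeguard. When the blinded OC and the CCE/CTC report disagree, a second, unblinded OC is done (8.11.1, Appendix C3), and Table 3 accepts findings from either pass.

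**The concern.** The plan grades the quality of its reference exam and then, in the text that can be read, does nothing with the grade. A Fair OC is by definition completed, so it cannot fall under the only OC exclusion. Yet the scale says it is too soiled to be relied on.

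Two errors follow. A lesion that CCE or CTC correctly saw, and that the soiled OC fails to show on both passes, becomes a false positive and drops out of confirmed yield. A lesion missed by the index exam and by the soiled OC becomes a true negative. The first lowers PPV, specificity and yield. The second flatters NPV and can flatter sensitivity. The accuracy measures are the most exposed, because their analysis set carries no OC condition at all.

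**Working it through.** **1. The plan's own figure.** Section 9.1 claims more than 80% power with yields of 25% (CCE) and 15% (CTC), a 5-point margin, 160 per arm and 10% attrition (160 × 0.9 = 144 per arm). At 144 per arm, SE = √(0.25×0.75/144 + 0.15×0.85/144) = 0.0468. Fixed-sample power at one-sided 5% is Φ(0.15/0.0468 − 1.645) = 94.1%. Simulating the 98%/96% posterior rule with looks at 36/72/108/144 per arm gives 93.7%. No prior is stated, so flat Beta(1,1) priors were assumed. The power claim is met and is not in dispute.

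**2. Accuracy measures.** The screening study in Table 1 (polyps of 6 mm or more) gives OC yield 28%, used here as prevalence, CCE sensitivity 81% and specificity 93%. Two inputs are not in the documents and are assumed: f, the share of OCs that are inadequate (5-15%), and m, the share of lesion-positive subjects that such an OC leaves unconfirmed after any second pass (30-50%). Write u = f × m, so u runs from 0.015 to 0.075.

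Starting cells:
- TP = 0.28×0.81 = 0.2268
- FP = 0.72×0.07 = 0.0504
- FN = 0.28×0.19 = 0.0532
- TN = 0.72×0.93 = 0.6696

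A share u of TP moves to FP, and a share u of FN moves to TN.

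| | u = 0 | u = 0.015 | u = 0.075 |
|---|---|---|---|
| Confirmed yield (TP) | 22.7% | 22.3% | 21.0% |
| PPV = TP/(TP+FP) | 81.8% | 80.6% | 75.7% |
| Specificity = TN/(TN+FP) | 93.0% | 92.6% | 90.9% |
| Rise in false positives | – | 7% | 34% |

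Worked for u = 0.075: 0.2268×0.075 = 0.0170 moves to FP, so PPV = 0.2098/0.2772. Then 0.0532×0.075 = 0.0040 moves to TN, so specificity = 0.6736/0.7410. NPV rises from 0.6696/0.7228 = 92.6% to 0.6736/0.7228 = 93.2%.

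One value of m for both routes is a simplification. Discordant positives get a directed second look and shared misses get none. In the limiting case where every discordant lesion is recovered but shared misses keep u = 0.075, PPV is unchanged and apparent sensitivity rises to 0.2268/(0.2268+0.0492) = 82.2%.

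**3. Primary comparison.** If the loss is the same proportion in each arm, observed yield is p(1 − u). The same simulation gives:

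| f, m | Yields CCE/CTC | Difference | Power | Chance of claiming non-inferiority when true yields are 15% v 20% |
|---|---|---|---|---|
| none | 25 / 15% | 10.0 | 93.7% | 6.6% |
| 5%, 50% | 24.4 / 14.6% | 9.75 | 93.5% | 7.0% |
| 10%, 50% | 23.75 / 14.25% | 9.5 | 93.1% | 7.3% |
| 20%, 50% | 22.5 / 13.5% | 9.0 | 92.6% | 8.0% |

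The last row lies beyond the upper end used in step 2. At f = 10%, m = 50% the loss is 144×0.25×0.05 = 1.8 true positives in the CCE arm and 144×0.15×0.05 = 1.1 in the CTC arm. The 6.6% starting value depends on the assumed prior and is not part of this point; only the change matters here.

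**4. Restricting to adequate OCs.** Removing a share f from both arms leaves non-inferiority power of 92.5% (f = 5%), 91.5% (10%) and 88.5% (20%).

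**The case against.** The second OC is the strongest answer. The operator holds the central report when looking again, so a false positive of this kind requires a lesion to be missed twice, the second time on a directed search. This stands in part, and it is why the upper figures in step 2 are probably too high. It does not close the gap: Section 8.0 has the report reviewed immediately after the blinded exam, so the same preparation applies, and agreement on a miss triggers nothing.

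A reader might infer that every Poor OC is also kept. The documents do not settle that. Appendix C3 expects the entire colon to be seen, so a site could record a Poor OC as not done or as a major deviation. Only Fair is clear. A soiled colon in a subject who followed instructions is not plainly a protocol violation, so the deviation clause is weak cover for Fair.

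A reader might also infer that the plan contains no analysis by OC quality. That cannot be said. The additional analyses in the synopsis, Section 8.4 and most of the list in 9.3 are redacted, and Appendix E does not present its sensitivity analyses as a closed list. The population rule in 9.5 and Table 3 are fully visible, and the gap lies there.

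Subjects with no OC at all, whom the mITT definition admits, are a separate missing-reference problem.

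**Conclusion.** The gap is real for Fair OCs and ambiguous for Poor ones. Its main effect is on the secondary measures: PPV and specificity are biased down, and shared misses are credited as true negatives. Under the assumed rates, PPV falls by about 1 to 6 points, specificity by about 0.4 to 2 points and yield by under 2 points. The rates behind these figures are not in the documents. That lost lesions leave the yield is itself an inference from 8.2 read with Table 3, since no yield formula is written out.

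A reader might go further and infer that the gap makes the non-inferiority test lenient. The documents do not support that as a general statement. Appendix C1 gives both arms the same OC preparation, so the loss should be roughly proportional and pull the difference toward zero. That mildly helps a non-inferiority claim only if CCE is truly worse (6.6% to 7.3% at the boundary for f = 10%, m = 50%). Under the plan's own assumption that CCE is better, it mildly reduces power (93.7% to 93.1%). The stated power is not threatened. This is a cheap improvement, not a flaw in the primary design.

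**What to change.** In 9.5, define an evaluable reference standard: an OC that visualized the entire colon, with overall cleansing Good or Excellent on Appendix C4. Apply it identically in both arms and without regard to the CCE/CTC result. Because the second OC is done only on disagreement, that last condition requires judging the rule on the blinded OC; Table 3 can still use findings from both passes.

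Use this set for sensitivity, specificity, PPV and NPV, and report the mITT version alongside. Add one pre-specified supportive analysis of primary yield in the same subjects. Leave the primary population unchanged, so its power is unaffected.

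The cost is wording in 9.5 and a few extra tables from a grade already on the CRF. The evaluable tables will hold somewhat fewer subjects (5-15% under the assumption above), including some whose lesion was matched despite poor preparation. The mITT tables keep those subjects in view.

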**8.2 Primary Effectiveness Endpoint**

The primary effectiveness endpoint is the diagnostic yield (proportion of subjects shown to have an actionable lesion, defined as any polyp or mass lesion  $\geq 6$  mm) by capsule colon endoscopy as compared to computed tomographic colonography. Diagnostic yield of CCE and CTC will be calculated in relation to the confirmatory OC results.

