## 9.0 Statistical Analysis

### 9.1 Sample Size Determination

The sample size is estimated based on the primary non-inferiority hypothesis under a Bayesian adaptive design. Interim assessments will be performed at every 80 subjects (40 per arm) with a maximum of 320 subjects (160 per arm). Early success will be claimed if the pre-defined success criterion is met.

The following parameter assumptions are used in the estimation, based on prior literature (15).

- Predicted CCE diagnostic yield: 25%
- Predicted CTC diagnostic yield: 15%
- Noninferiority hypothesis with a 5% margin
- Accounting for approximately 10% attrition

With the assumptions, a total of 320 subjects (160 per arm) with interim assessments at every 80 subjects (40 per arm) will provide more than 80% power to test the primary hypothesis at the significance level of 5%.

Note that the expected sample size will be smaller than 320 with the adaptive Bayesian design since an early interim claim for success is possible. Additionally, if non-inferiority is proven, superiority will also be tested (which is not statistically powered at 80%).

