### Step 4: Reader Sends CCE Results to the Sponsor

All findings will be saved as thumbnails, with detailed description of each finding, to create a detailed GRML file. Central readers will provide a report of their findings to the sponsor within 2 weeks of capsule ingestion in order to allow subjects to return within 5 weeks capsule ingestion procedure to

undergo confirmatory OC. The central readers will be required to return the following items to the sponsor:

- Signed RAPID® report
- GRML file
- Case Report Form (CRF)

*Step 5: Sponsor Sends CCE Results back to the Site*

Upon receipt, the sponsor will send the signed RAPID report, the signed cleansing evaluation form, and the case report form to a designated person at the relevant site. Local reader results will be read within 2 weeks and kept at the subject binder until confirmatory OC. The results will not be disclosed to the physician performing the colonoscopy until after the blinded colonoscopy is complete.

The GRML file will be provided to the relevant site upon specific request.

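### Section 9.5 removes centrally read subjects who withdraw or have no OC, so the primary yield depends on who attends OC; the comparison is biased if that loss depends on the index result and differs by arm

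*Combined protocol and SAP*

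**What the plan says.** Section 8.2 defines the primary endpoint as the "proportion of subjects shown to have an actionable lesion, defined as any polyp or mass lesion" of at least 6 mm, by CCE compared with CTC, calculated in relation to the confirmatory OC. Section 8.11.1 ties yield to the polyp-matching algorithm. It points to Appendix D, but the algorithm is in Appendix E.

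Section 9.5 bases the primary analysis on randomized subjects without major protocol deviations who meet none of four criteria. Criterion 1 is withdrawal. Criterion 3 is "Optical colonoscopy could not be done". Neither depends on whether the index test was completed and read, or on what it showed. The same section plans a confirmatory analysis on an mITT set of all randomized subjects with CTC or CCE. It does not say how yield is scored there when OC is missing.

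OC is planned for every subject, positive or negative, within 5 weeks of the index test. Section 9.1 lists "Accounting for approximately 10% attrition", with no split by cause, arm or index result. Appendix A4, Step 5 says of the reading results: "The results will not be disclosed to the physician performing the colonoscopy until after the blinded colonoscopy is complete". Appendix B4, Step 6 repeats this for CTC. The flow chart in the synopsis has a step before OC saying that blinding to the CCE/CTC results is kept, without saying for whom.

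**The concern.** Yield counts lesions that the index test shows and OC confirms. OC can remove a subject from the numerator, but it cannot add one whose index exam reported nothing matchable. For that subject the contribution is already settled at zero, yet criteria 1 and 3 take the subject out of the denominator.

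The observed yield then depends on attendance at a later procedure. If index-negatives miss OC more often than index-positives, the yield is too high. If index-positives miss it more often, the yield is too low. When this pattern differs between arms, the error passes into the difference that is tested against a 5-point margin. Extra loss of CCE index-negatives favours a false claim of non-inferiority. The same loss in the CTC arm costs power.

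**Working it through.** **1. The plan's own figure.** Inputs from section 9.1: CCE 25%, CTC 15%, margin 5%, attrition 10%, 160 per arm.

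n per arm = (z_α + z_β)² × (0.25×0.75 + 0.15×0.85) / (0.25 − 0.15 + 0.05)² = (z_α + z_β)² × 0.315/0.0225.

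- One-sided 5%: (1.645 + 0.842)² × 14 gives 87, or 97 after dividing by 0.9.
- One-sided 2.5%: 110, or 123 after dividing by 0.9.
- With 144 evaluable per arm (160 × 0.9), power is 94.1% or 89.4%. A simulation of the Bayesian design (looks at 36, 72, 108 and 144 per arm, thresholds 98/98/98/96%) gives 93.7%. The plan states no prior, so Beta(1,1) is assumed.

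The stated power of more than 80% is met. The problem is not sample size.

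**2. Bounds from the planned attrition.** Take 160 per arm with 16 (10%) lacking OC.

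| Who lacks OC | CCE, true 40/160 = 25% | CTC, true 24/160 = 15% |
|---|---|---|
| Only index-negatives | 40/144 = 27.8% | 24/144 = 16.7% |
| Random | 25.0% | 15.0% |
| Only would-be true positives | 24/144 = 16.7% | 8/144 = 5.6% |

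The outer rows are extremes, not forecasts. Random loss moves nothing.

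**3. Graded scenarios.** Let ip be the index-positive rate, c the confirmation rate, and sn and sp the skip rates in index-negatives and index-positives. Under the 9.5 rule:

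yield = ip·c·(1−sp) / [ip·(1−sp) + (1−ip)·(1−sn)].

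All of these rates are assumptions. With ip 25%, c 80% and sp 5%, the true yield is 20%. The observed yield is 20.0, 20.8, 21.7 and 22.7% for sn of 5, 10, 15 and 20%. If matchable findings are commoner but less often confirmed (ip 50%, c 40%), sn of 20% shifts the yield by 1.7 points instead of 2.7.

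**4. Effect on the claim.** Null boundary: CCE 15%, CTC 20%, 160 randomized per arm, one look at 96%, Beta(1,1) priors, sp 5%. With c 80% in both arms, CCE ip = 0.15/0.80 = 18.75%. At sn 20% the CCE yield is 0.1425/(0.1781 + 0.6500) = 17.2%, a shift of 2.2 points. The ranges below cover a CTC index-positive rate of 25% to 50%, with the same confirmation rate in both arms (80% down to 40%).

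| Index-negative skip, CCE vs CTC | False-claim rate |
|---|---|
| 5% vs 5% | about 4% |
| 10% vs 5% | 5-6% |
| 15% vs 5% | 7-8% |
| 20% vs 5% | 9-11% |
| 10, 15 or 20% in both arms | about 3.6-4.2% |

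With all four looks the rate is 6.6% under random loss. If only CCE index-negatives skip and CTC loss is random, it becomes 8.8% (5% of CCE subjects missing) or 11.9% (10% missing). It is 5.4% if only index-negatives skip, at 10%, in both arms. The 6.6% baseline depends on the assumed prior and is a separate matter.

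**5. Does keeping these subjects cure it?** Estimate yield per arm as P(matchable finding among centrally read) × P(confirmed among those who had OC). In the CCE example this is 0.1875 × 0.80 = 15.0% whatever sn is. With c 80%, the simulated false-claim rate for CCE skip rates of 5, 15 and 20% against 5% is 4.5, 4.3 and 4.2%. Complete-case gives 4.1, 7.7 and 10.7%.

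Keeping index-negatives but dropping index-positives without OC is not enough. Treating every index-positive as a would-be true positive, random 10% loss then gives 0.225/0.975 = 23.1% for CCE instead of 25%, and 0.135/0.985 = 13.7% for CTC instead of 15%. The second group needs its own rule.

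**The case against.** Four objections have weight.

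- **The mITT analysis.** A reader might infer that the plan loses these subjects altogether. It does not, because the mITT set keeps them. But that analysis is only confirmatory, and without a scoring rule for a missing OC it cannot show whether the primary result is biased.
- **Known zero.** It is tempting to say that every index-negative subject's yield is already known to be zero. That is certain only when no matchable finding is reported. The true-positive cell of Appendix E needs a match and a reference polyp of at least 6 mm, and the reference may be the OC polyp. A 4 mm index polyp matched to a 7 mm OC polyp could therefore count. The first step of Appendix E may restrict both methods to polyps of at least 6 mm, but the text is ambiguous.
- **Mechanism.** A reader might infer that subjects learn their result and skip OC because of it. No section says so. The flow chart points the other way, and local results stay in the subject binder until OC. Section 8.10.3, where "neither the subject nor the investigator will be blinded to the assigned study arm", concerns knowledge of the arm, not of the result. What stands is that the express non-disclosure rule names only the physician performing OC, so disclosure to subjects is not expressly barred.
- **Difference by arm.** Result-dependent skipping that is equal in both arms does not raise the false-claim rate, and nothing in the documents predicts a difference. Milder differences do little: 5.8% for 10% against 5%, and 5.2% for 12% against 8%. With c 80%, the 15% and 20% rows imply total CCE loss of about 13% and 17%, above the planned 10% for that arm, although loss pooled over the arms stays near 10%.

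**Conclusion.** The point holds in conditional form. Criteria 1 and 3 discard outcomes that are already determined and leave the primary contrast exposed to attendance at OC. Under random loss, or under result-dependent loss that is equal in both arms, the false-claim rate does not rise. If CCE index-negatives miss OC at 10 to 20% against 5% in CTC, it rises from about 4% to between 5% and 11% at a single final look. These figures rest on assumed skip, index-positive and confirmation rates and on flat priors. The documents give only the overall attrition.

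The documents do not support saying that the bias is present, that subjects are told their results, or that every index-negative subject's yield is known. The change is still worth making before the data are seen: the mITT set as written does not resolve the matter, and the trial already holds the central reads that would.

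**What to change.** - In 9.5, do not apply criteria 1 and 3 to subjects whose CCE or CTC was completed and centrally read. Leave the separate exclusion for major protocol deviations in place, since withdrawals under 8.8 can include significant violations and emerging exclusion criteria.
- Score exams with no finding that could become a true positive under Appendix E as no yield. State whether index findings below 6 mm can become true positives. Unless Appendix E is clarified to exclude them, treat them as potentially matchable.
- In 9.2, estimate each arm's yield as P(matchable finding among centrally read subjects) × P(confirmed among those with a matchable finding who had OC). The posterior is the product of two Beta posteriors per arm.
- Apply the same scoring in mITT.
- As sensitivity analyses, report the complete-case result and the result with all unverified positives set to not confirmed. Under random 10% loss at the design yields, the latter gives 22.5% against 13.5%, with simulated power of 94.6%.
- Tabulate missing OC by arm and index result.

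The cost is SAP wording and a few lines of code, with no new data or subjects. The downside is small: the estimator assumes that unverified positives are confirmed at the same rate as verified ones in their arm. The second sensitivity analysis tests that assumption.
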